## 6.2 PREPARATION/HANDLING/STORAGE/ACCOUNTABILITY

- The Investigator or designee must confirm appropriate temperature conditions have been maintained during transit for all study intervention received and any discrepancies are reported and resolved before use of the study intervention.
- Only subjects led in the study may receive study intervention and only authorized site staff may supply or administer study intervention. All study intervention must be stored in a secure, environmentally controlled, and monitored (manual or automated) area in accordance with the labelled storage conditions with access limited to the Investigator and authorized site staff.
- The Investigator, institution, or the head of the medical institution (where applicable) is responsible for study intervention accountability, reconciliation, and record maintenance (i.e., receipt, reconciliation, and final disposition records).
- Further guidance and information for the final disposition of unused study interventions are provided in the relevant pharmacy manual.

## 6.3 MEASURES TO MINIMIZE BIAS: RANDOMIZATION AND BLINDING

Not applicable; this is an open-label study.

## 6.4 STUDY INTERVENTION COMPLIANCE

Study intervention will be administered at the study site in the presence of the Investigator or designee, as per the SoA (Section 1.3).

A record of the dose of SUPLEXA administered to each subject must be maintained and reconciled with study intervention and compliance records. Minimally, drug start and stop date and time, including dates for drug delays will also be recorded in the electronic case report form (eCRF).

## 6.5 DOSE LIMITING TOXICITY CRITERIA

A DLT is defined as the occurrence or start of any of the events listed below during the treatment of the first 3 subjects in each cohort that are assessed as related to study intervention (SUPLEXA) by the Investigator or the Sponsor. An AE should not be considered as a DLT if it can reasonably be attributed to underlying disease, disease progression, concomitant medications, or other extraneous causes. Worsening of pre-existing medical illness could be due to study intervention and should not be excluded from consideration as a DLT.

The first 15 subjects will be assessed for DLT. For each subject, the DLT assessment period will comprise of 2 parts as follows (Refer to [Figure 5](#)):

- The first DLT assessment period – 1 week after the first dose (prior to administration of the second dose).
- The second DLT assessment period - 1 week after the second dose (prior to the administration of the 3rd dose)

Subjects who withdraw before the end of the DLT assessment period for reasons other than DLTs will be replaced.

All toxicities will be graded by the local site Investigator using National Cancer Institute (NCI) common terminology criteria for adverse events (CTCAE) v5.0.

The following will be considered DLTs:

### Haematologic:

1. Grade 4 neutropenia lasting for  $\geq 7$  days.
2. Febrile neutropenia is defined as ANC  $<1000/\text{mm}^3$  with a single temperature of 38.3°C (101°F) or a sustained temperature of 38°C (100.4°F) for  $>1$  hour.
3. Grade 4 thrombocytopenia, or Grade 3 thrombocytopenia associated with clinically significant bleeding.
4. Grade 4 anaemia unless there is an alternative explanation e.g., bleeding, etc.

### Non-haematologic:

1.  $\geq$  Grade 3 non-haematologic toxicity, except for the following Grade 3 events that are considered either not an adverse event or events that could be managed with standard of care:
  - a) Grade 3 inflammatory reaction attributed to a local anti-tumour response (e.g., inflammatory reaction such as pain, irritation, or localized rash at sites of metastatic disease, lymph nodes, etc.).
  - b) Grade 3 fatigue lasting  $\leq 3$  days.
  - c) Grade 3 diarrhea, nausea, or vomiting lasting  $\leq 3$  days without or with use of anti-emetics or anti-diarrheals per standard of care.
  - d) Grade 3 rash and/or pruritis without use of corticosteroids or anti-inflammatory agents per standard of care.

2. Any Grade 3 or Grade 4 non-haematologic laboratory value if:
  - a) Clinically significant medical intervention is required to treat the subject and does not resolve within 72 hours, or
  - b) Potential drug-induced liver toxicities with laboratory parameters as described below
    - $\geq$  Grade 3 and above elevation in ALT or AST if an alternative explanation other than the study intervention is not available.
    - $\geq$  Grade 3 and above elevation of total bilirubin of any duration if an alternative explanation other than the study intervention is not available.
    - Grade 2 elevation AST/ALT with concurrent elevation of total bilirubin  $>2 \times$ ULN or INR  $>1.5 \times$ ULN if an alternative explanation other than the study intervention is not available.

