Disease evaluation by Response Evaluation Criteria in Solid Tumours (RECIST) v1.1 and immune RECIST (iRECIST) (solid tumours only)		X h			X i		X i	X i	X i	h. Scans within 4 weeks of screening will be accepted. i. Using standard of care scan schedule for the specified solid tumour. The first radiographic scan after receiving SUPLEXA will be performed at Week 6-12 weeks after the 1st SUPLEXA infusion and thereafter every 6-12 weeks depending on tumour type and as clinically indicated per investigator's discretion.

Study period	Screening		Treatment Period (Weekly dosing)		TREATMENT GAP	Treatment Extension Period	Follow Up after last dose		Notes	
			SUPLEXA Batch 1							
Study Treatment Week	-5	-5 to -1	First 3 infusions	Additional doses 		Doses 				
Visit Window (days)		±2		±2		60	-1 to +7	±5		
			Week 0 Day 1/ Baseline	1, 2			Every 8 weeks up to 48 weeks from last dose	EOS/ET	End of Study (EOS) will be conducted within 30d for all subjects who completed the study per protocol; Early termination (ET) visit will be conducted within 30d or subjects who withdraw from the study prematurely.	
Disease evaluation for haematologic malignancies only		X		X*		X*	X*	X	*As clinically indicated, may also be conducted every 4 weeks, starting 4 weeks after the 3 rd dose	
Complete blood count (CBC) with differential and blood chemistry	X		X j	X j, k	X j	X j	X	X	Refer to Table 5 for list of parameters to be evaluated j. Predose k. Repeat at baseline in local hospital lab for stat results, and central lab sample to be shipped	
Collect blood for pharmacodynamic immune assessments, including cytokines			X	X	X	X	X l		Refer to Section 8.4 for list of parameters to be evaluated l. collected where possible post dose	

Study period	Screening		Treatment Period (Weekly dosing)		TREATMENT GAP	Treatment Extension Period	Follow Up after last dose		Notes	
			SUPLEXA Batch 1							
Study Treatment Week	-5	-5 to -1	First 3 infusions	Additional doses 		Batch 2				
			Week 0 Day 1/ Baseline	1, 2		Doses 				
Visit Window (days)		±2		±2	±2	-1 to +7	60	-1 to +7	Every 8 weeks up to 48 weeks from last dose	EOS/ET
Serology		X m							Refer to Table 5 for list of parameters to be evaluated	

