### 3 OBJECTIVES AND ENDPOINTS

Objectives	Endpoints
Primary	

 
To assess safety and tolerability of SUPLEXA in subjects with malignant solid tumour and haematologic malignancies.
 
	
 
Incidence of dose limiting toxicities (DLTs) (as described in Section 6.5.1).
 
Incidence of adverse events (AEs), and serious adverse events (SAEs) overall, by severity, by relationship to each study intervention, and those that led to discontinuation of study intervention.
 

Secondary 
 
Solid tumours cohort: To assess the efficacy of SUPLEXA in subjects with malignant solid tumour as assessed by the Investigator based on response evaluation criteria in solid tumours (RECIST) v1.1 or by changes in tumour-derived blood biomarkers.
 
Haematologic malignancies cohort: To assess the efficacy of SUPLEXA in subjects with haematologic malignancies (multiple myeloma, lymphoma, and chronic lymphocytic leukemia).
 
	
 
Objective response rate (ORR) defined as the proportion of subjects with best overall response (BOCR) of either a complete response (CR) or partial response (PR).
 
Time to Progression (TTP).
 
Objective response rate as defined by standard of care.
 

Exploratory 
 
Exploratory efficacy outcomes
 
	
 
Duration of Response (DOR)
 
Time to Response (TTR)
 
Clinical Benefit Rate (CBR) defined as CR + PR + stable disease (SD).
 
Progression-free Survival (PFS).
 
Overall Survival (OS).
 
Solid tumours cohort: Change in plasma biomarkers.
 
Haematologic malignancies cohort: Response-relationship with correlative biomarkers in blood and bone marrow including immunophenotyping of circulating PBMC and/or bone marrow, gene expression, mutational analysis.
 

Objectives	Endpoints

 
• To evaluate anti-tumor activity of SUPLEXA by based on modified RECIST v1.1 for immune based therapeutics (iRECIST)
 
	
 
• iORR
 
• iPFS
 
• iDOR
 
• iDCR
 

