### Diagnostic Assessments

12. A performance status  $\geq 2$  on the Eastern Cooperative Oncology Group (ECOG) Performance Scale (solid tumours cohort) or Karnofsky performance scale of  $\geq 60$  (haematologic malignancies cohort)

13. Does not demonstrate adequate organ function as defined as an excursion beyond the acceptable limits below. All screening laboratories should be performed at screening and on the day of first administration of study therapy.

System	Laboratory Value
Haematological	
Absolute neutrophil count (ANC)	$\leq 50\%$ lower limit of normal (LLN)
Lymphocyte (WBC)	$\leq 50\%$ LLN
Platelets	$<100 \times 10^9/\text{L}$
Haemoglobin	$\leq 9 \text{ g/dL}$ or, $\leq 5.6 \text{ mmol/L}^*$
Renal	

Creatinine OR	>1.5 times upper limit of normal (ULN) OR
Measured or calculated**creatinine clearance (CrCl) Glomerular filtration rate (GFR) can also be used instead of creatinine or CrCl	< 45 mL/min for subject with creatinine levels
Hepatic	
Total bilirubin	> 1.5 × ULN OR direct bilirubin ≥ULN for subjects with total bilirubin levels > 1.5× ULN
Aspartate aminotransferase (AST) and alanine aminotransferase (ALT)	>2.5 × ULN (> 5 × ULN for subjects with liver metastases)

\* Criteria must be met without erythropoietin dependency and without packed red blood cell (pRBC) transfusion within last 2 weeks

\*\* Creatinine clearance should be calculated per institutional standard.

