## 10.2 APPENDIX 2: CLINICAL LABORATORY TESTS

- The clinical laboratory tests detailed in [Table 5](#) will be performed by a central laboratory at timing/frequency detailed in the SoA (Section [1.3](#))
- Additional tests may be performed at any time during the study as determined necessary by the Investigator or required by local regulations.
- Investigators must document their review of each laboratory safety report

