**Table 5: Clinical Safety Laboratory Tests**

Hematology	
White blood cell count (WBC) with differential (neutrophils, lymphocytes, monocytes, eosinophils, basophils – absolute and %)	Red blood cell (RBC) RBC Indices: MCV, MCH, %Reticulocytes
Haemoglobin	Haematocrit
Platelet count	
Clinical Chemistriesa	
Electrolytes: Sodium, Potassium, CO 2 or bicarbonate, Chloride, Calcium, Magnesium, Phosphorus,	
Liver function: Alkaline Phosphatase, alanine aminotransferase (ALT), aspartate aminotransferase (AST), Total Bilirubin	
Renal function: Blood Urea Nitrogen, Creatinine, Creatine Kinase, calculated Creatinine Clearance Cockcroft-Gault	
Other: Albumin, lactate dehydrogenase (LDH), non-fasting Glucose, uric acid, lactate dehydrogenase, total protein, total cholesterol, and triglycerides	
Urinalysis	
Basic Urinalysis (dipstick, including macroscopic appearance, bilirubin, blood, colour, glucose, ketones, leukocyte esterase, nitrite, pH, protein, specific gravity, urobilinogen;	Full urinalysis (dipstick plus microscopic evaluation) to be performed only at the Screening and End of Study visits). A reflex microscopic urinalysis should be performed if the result of the urinalysis is abnormal or at the discretion of the PI or delegate.
Other Study-Specific Laboratory Assessments	
Serum and urine human chorionic gonadotropin (hCG) pregnancy test	Serology
Syphilis screening test (rapid plasma regain)	HIV antibody, hepatitis B surface antigen (HBsAg), hepatitis C virus antibody or HCV RNA (qualitative)

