### Amendment 1.0; 09 November 2021

#### Overall Rationale for the Amendment:

#### Summary of Changes (in order of appearance)

Section Number and Name	Description of Change	Rationale for Change
1.1 Synopsis (Overall Design) 4.1.2 Treatment Period	
 
Clarify staggering procedure
 
Clarify determination for treatment extension
 
	
 
To align with Study Schema and for clarity
 
Per request of HREC
 

1.3 Schedule of Activities 6.8.1 Prophylaxis	
 
Clarify reason and timing of treatment prophylaxis
 
	
 
Per request of HREC
 

2.3.1 Risk Assessment 6.6 Toxicity Management 10.6 CSR Toxicity Treatment Guidelines 10.7 TLS Toxicity Management	
 
Cross reference to CRS and TLS toxicity treatment guidelines which were added (Appendices 6 and 7)
 
For TLS, clarify summary of risk
 
	
 
Per request of HREC
 

5.2 Exclusion Criteria	
 
Add exclusion of subject at high risk for developing TLS
 
	
 
As a safety precaution
 

5.2 Exclusion Criteria 10.2 Appendix 2 Clinical Safety Laboratories	
 
Delete exclusion criteria relating to coagulation
 
Delete coagulation parameters from laboratory tests
 
	
 
As biopsies will not be collected as part of this study no need to measure coagulation
 

7.1 Study Stopping Rules	
 
Add a study stopping criteria associated with DLTs
 
Clarify language around study stopping criteria
 
	
 
Per request of HREC
 

8.4 Pharmacodynamics and Correlative Biomarkers	
 
Moved text on disease biomarkers under this section and delete immunogenicity which is not assessed
 
	
 
For consistency and clarity
 

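### The hepatic DLT definition relies on INR, but no INR or PT is scheduled, so one limb of the primary DLT endpoint is ascertained only if an investigator chooses to order the test

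*Combined protocol and SAP*

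**What the plan says.** The first-listed primary endpoint in Section 3 is "Incidence of dose limiting toxicities (DLTs) (as described in Section 6.5.1"). The criteria themselves are in Section 6.5. Among the liver criteria in non-haematologic item 2b, one bullet covers "Grade 2 elevation AST/ALT with concurrent elevation of total bilirubin" above 2×ULN, or INR above 1.5×ULN, where no explanation other than the study intervention is available.

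The protocol's laboratory tests are those in Appendix 2, Table 5. Its liver line reads "Liver function: Alkaline Phosphatase, alanine aminotransferase (ALT), aspartate aminotransferase (AST), Total Bilirubin". No other Table 5 category contains INR, PT or aPTT. In the Schedule of Activities the blood safety row is "Complete blood count (CBC) with differential and blood chemistry", which refers to Table 5 for its content; there is no coagulation row.

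Section 6.5 defines two DLT windows, one week after dose 1 and one week after dose 2, and names the first 15 subjects for assessment. Section 6.5.1 then applies the DLT rules to every subject: a DLT that has not resolved within 3 weeks, or a second DLT, ends treatment.

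**The concern.** A component of a primary endpoint should be measured in the same way in every subject who can contribute to it. Here one alternative in the DLT definition depends on an analyte that the plan never schedules. A subject with Grade 2 AST or ALT, bilirubin at or below 2×ULN and a raised INR has the pattern the bullet describes, but will be recorded as DLT-free unless someone orders an INR. Two things are at stake: the completeness of the primary safety count, and the dose 2 and dose 3 decisions in Section 6.5.1, which depend on whether a DLT was recorded.

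**Working it through.** The plan has no figure to reproduce here: about 60 subjects are planned, with no event rate, power or error rate behind the DLT count. The check is whether each analyte in the bullet can be found in the scheduled tests.

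| Analyte in the bullet | In Table 5? | In a Schedule of Activities row at the dosing visits? |
|---|---|---|
| AST/ALT | Yes | Yes (chemistry, predose) |
| Total bilirubin | Yes | Yes (chemistry, predose) |
| INR (or PT) | No | No |

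Other possible sources do not supply it. The eligibility laboratory table (Section 5.2, item 13) has no coagulation value. Section 8.4 covers immune phenotype, cytokines and tumour markers. Elsewhere in the current text INR and PT appear only as glossary abbreviations. Scheduled INR measurements per subject are therefore 0 (baseline) + 0 (first window) + 0 (second window) = 0.

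Next, take a subject with Grade 2 AST/ALT judged related, with no other explanation:

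- Bilirubin above 2×ULN, any INR: the bullet is met, and scheduled samples show it.
- Bilirubin at or below 2×ULN, INR at or below 1.5×ULN: the bullet is not met, and leaving INR out changes nothing.
- Bilirubin at or below 2×ULN, INR above 1.5×ULN: the bullet is met, but this is seen only if an INR was ordered.

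Only the third case can be misclassified, and only from DLT to no DLT. If p is the chance that a subject falls in that case and d the chance that an INR is then ordered, the expected under-count is p × (1 − d) per subject. It runs from 0 (d = 1) to p (d = 0). The documents give neither p nor d.

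The amendment history offers a likely origin, as background only. Amendment 1.0 records "Delete coagulation parameters from laboratory tests", with the reason "As biopsies will not be collected as part of this study no need to measure coagulation". That reason does not mention the DLT criterion. The inconsistency itself lies wholly in current text: Section 6.5 against Table 5 and the Schedule of Activities.

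The same bullet has a second wording problem. It sits under item 2, whose opening line limits the item to Grade 3 or Grade 4 laboratory values, while the bullet concerns Grade 2. Read literally, a Grade 2 case might not qualify through either limb. Scheduling INR would not resolve this.

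**The case against.** The strongest reply is that the limb can still be met. Section 10.2 says "Additional tests may be performed at any time during the study as determined necessary by the Investigator or required by local regulations". Section 8.2.4 requires non-protocol local results to be recorded when they are clinically significant or change management. Appendix 3 obliges the investigator to arrange further measurements when medically indicated or when the sponsor asks. A reader might infer that the criterion is impossible to meet; these provisions show that it is not. But none of them names INR or ties it to a Grade 2 transaminase rise, so they make ascertainment discretionary rather than uniform.

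Other limits stand:

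- **The path is narrow.** It needs Grade 2 AST/ALT, bilirubin not above 2×ULN, a raised INR and no other explanation. The Grade 3 or higher AST/ALT and bilirubin bullets can be assessed from scheduled samples.
- **Much of the window may have closed.** Section 2.3.1 reports more than 15 subjects with 3 to 6 doses by September 2022, no treatment-related events and nothing notable in the laboratory data. This lowers the likely effect on the first 15. It does not dispose of the point, because Section 6.5.1 still applies the rules to every subject and the split by cohort is not given.
- **A baseline INR is not needed to cross the threshold**, which is relative to ULN. Baseline matters only for separating a pre-existing elevation from a new one when an alternative explanation is considered.

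Two further inferences are tempting but unsupported. One is that the gap weakens the DLT-based hold in Section 7.1. That hold needs DLTs of Grade 4 or higher in two subjects, which an event qualifying through Grade 2 AST/ALT plus INR does not supply on its stated terms. The other concerns eligibility item 13, which refers to "direct bilirubin ≥ULN for subjects with total bilirubin levels" although Table 5 has no direct bilirubin. Total bilirubin above 1.5×ULN already excludes the subject under the preceding alternative, so no decision turns on the missing test.

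**Conclusion.** The inconsistency is real and limited. Section 6.5 makes INR part of the primary DLT definition, and the measurement plan does not collect it. As written, this limb is ascertained by investigator choice, and a test not taken can only remove events from the DLT count. The under-count has no computable size and is probably small. A reader might express it as one event lost among the first 3 or the first 15 subjects, but that assumes an event for which the documents give no rate, so it is not evidence of magnitude.

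The conclusion assumes that Table 5 and the Schedule of Activities are the full list of required tests, and that the Grade 2 bullet is meant to operate despite its Grade 3 or 4 parent line.

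**What to change.** Reconcile Section 6.5 item 2b with Table 5 and the Schedule of Activities so that every analyte in the DLT definition is measured in the DLT windows. One way to do this is PT/INR at baseline and as a reflex test when AST or ALT reaches Grade 2, using existing blood draws. Which clinical criterion stands is for the sponsor to decide; the requirement is that the definition and the measurements agree.

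In the same edit, reconcile the Grade 2 bullet with the opening line of item 2. For subjects already assessed, state in the report that INR was not scheduled, so that the DLT incidence is read with that limit in mind.

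If INR is measured, the cost is one routine coagulation tube per subject and occasional reflex tests. The wording changes cost only the amendment text.

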#### **6.5.1 Dose Modifications and Individual Stopping Rules due to DLT**

All eligible subjects are planned to receive a minimal cumulative dose of approximately 7.5 billion cells of SUPLEXA administered as target of 2.5 billion cells per individual SUPLEXA doses. The first 3 doses will be administered at least 1 week apart (unless delayed due to DLTs as described below) at Day 1 (baseline), Week 1 and Week 2.

During the study, the cumulative dose of study intervention will not be modified unless triggered by rules governing DLT (as described below); that is, subjects experiencing a DLT which does not resolve within 3 weeks or 2 DLTs may only receive 1 or 2 infusions, each 2.5 billion cells (for these subjects, cumulative dose may range between 2.5 billion cells to 5.0 billion cells).

[figure not shown]
The DSMB will convene to review all available data collected during the DLT assessment period(s) including Investigator's impressions and provide an additional layer of oversight. The DSMB will make recommendations to the Sponsor on enrolment modifications.

The rules below will apply independently to the solid tumours and haematologic malignancies in parallel and for each subject in the study.

1. Enrol a subject and administer 1st dose on Day 1. Assess for DLTs during the first DLT assessment period (1 week post 1st infusion).
  - a) No DLT, continue to 2nd dose at Week 1 (Day 8) – refer to item 2 below,
  - b) Subject experienced a DLT (per DLT criteria in Section 6.5) and the event resolved within 3 weeks to baseline levels (Grade 1 or lower)?
    - i) Yes, continue to 2nd dose – refer to item 2 below
    - ii) No, permanently discontinue study intervention and subject will continue to be followed-up as part of the study (unless withdraw consent and start other anti-cancer therapies) as described in Section 7.2.
2. Administer 2nd dose. Assess for DLTs during the 2nd DLT assessment period (1 week post 2nd infusion)
  - a) No DLT, continue to 3rd dose – refer to item 3 below

- b) Subject experienced a DLT (per DLT criteria in Section 6.5)
  - i) If first occurrence of DLT and the event resolved within 3 weeks to baseline levels (Grade 1 or lower)?
    - Yes, continue to 3rd dose – refer to item 3 below
    - No, permanently discontinue study intervention and subject will continue to be followed-up as part of the study (unless withdraw consent and start other anti-cancer therapies) as described in Section 7.2.
  - ii) If second occurrence of DLT in the same subject, permanently discontinue study intervention and subject will continue to be followed-up as part of the study (unless withdraw consent and start other anti-cancer therapies) as described in Section 7.2.
3. Administer 3rd dose and follow-up subject per SoA (Section 1.3).

Figure 5: Individual DLT Stopping Rules and Dose Modification of Study Intervention

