Dose limiting toxicity (DLT) assessment			DLT assessment period						consultation with Sponsor' Medical Monitor. Cumulative dose depends on the individual subject SUPLEXA manufacturing yield in batch 1 and in batch 2.	
			1	2					Refer to Section 6.5 for DLT criteria. DLT assessment periods: Period 1: 1 week after the 1st dose (before 2 nd dose administration) Period 2: 1 week after 2nd dose (before 2nd 3rd dose administration)	

Study period	Screening		Treatment Period (Weekly dosing)			TREATMENT GAP	Treatment Extension Period	Follow Up after last dose		Notes	
			SUPLEXA Batch 1								
Study Treatment Week	-5	-5 to -1	First 3 infusions		Additional doses 		Batch 2				
Visit Window (days)			±2	±2	-1 to +7		Doses 				
AE assessment	X	X	X s		X s	X s		Every 8 weeks up to 48 weeks from last dose	EOS/ET	
s. The first 3 subjects in each cohort will be monitored closely at the clinic for at least 6 hours after each of the first 3 weekly infusion and be contacted by phone on a daily basis (weekdays) between these weekly infusions for up to 5 days post the 3rd treatment.
 
During the observation period (as specified above), all subjects will be monitored for post infusion reaction(s) and AEs every 90 minutes.
 
Subsequent subjects will be monitored for 90 min post dose for post infusion reaction(s) and AEs.
 
If any of these subjects experience an adverse event of Grade 3 or greater, the longer in-clinic monitoring window of 6 hours post each of the first 3 weekly
	

Study period	Screening		Treatment Period (Weekly dosing)			TREATMENT GAP	Treatment Extension Period	Follow Up after last dose		Notes	
			SUPLEXA Batch 1								
Study Treatment Week	-5	-5 to -1	First 3 infusions		Additional doses 		Batch 2				
			Week 0 Day 1/ Baseline	1, 2			Doses 	Every 8 weeks up to 48 weeks from last dose		EOS/ET	
Visit Window (days)		±2		±2	-1 to +7	60	-1 to +7	±5	±28		
										infusions and daily calls will be reimplemented as done for the first 3 subjects.	
										t. For subjects with unresolved treatment-related toxicity at last dosing visit, follow as medically appropriate until stabilization.	
										Only SAEs that are believed related to study intervention will be collected.	

[figure not shown]

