### 6.1 STUDY INTERVENTION ADMINISTERED

ARM Name	Active
Primary Intervention Name	SUPLEXA therapeutic cells (referred to as SUPLEXA throughout)
Type	Autologous cellular therapy comprised of ex vivo activated autologous PBMC comprised predominantly of NK, NKT, $\gamma\delta$ T cells, and T cells of both CD8-positive and CD4-positive types stored in cryogenic media.
Dose Formulation	PlasmaLyte with 28 mM glucose, 3.5% human serum albumin, 50% EZ-CPZ (a proprietary cryopreservative medium) and 10% dimethyl sulfoxide
Unit Dose Strength	Billion cells
Dosage Level(s)	Each subject in each cohort will receive a target 2.5 billion SUPLEXA cells (range 1.3 to 3.1 billion cells) per infusion of 100 mL of cryogenic preservative solution.
Route of Administration	IV
Administration instructions	
Administer weekly (QW) <math>\pm 2</math> days for the first 3 weekly infusion and thereafter weekly with a range of -1 day to +7 days.
 
For prophylactic pre-treatment, refer to Section 6.8.1.
 
Thaw a SUPLEXA IV infusion bag.
 
Into the SUPLEXA IV infusion bag, slowly transfer approximately 250 mL (250 grams) of diluent PlasmaLyte (<math>\pm 20\%</math> is within the acceptable range; i.e., 200-300 grams or mLs). Allow the fluid to transfer by gravity.
 
Infuse each individual bag's full volume within 60 minutes into the subjects.
 
Where doses of 2 bags (5B cells) is given the same process and time is used. Thus, infusion of 2 bags is within 2 hours (120min).
 
Subjects may ambulate after infusion is complete.
 
For the first 3 weekly infusions:

ARM Name	Active
	
 
The first 3 subjects in each cohort will be monitored closely at the clinic for at least 6 hours after each of the first 3 weekly infusions and be contacted by phone on a daily basis (weekdays) between weekly infusions for up to 5 days post the 3rd treatment.
 
After the first three subjects , any subject receiving SUPLEXA will require a minimally 90minute (+/- 30min) post infusion observation and will be monitored for any AEs and immediate post infusion reaction(s).
 
 
Refer to Pharmacy manual for detailed administration instructions.

Sourcing	Autologous SUPLEXA therapeutic cells are manufactured, labelled, stored, and distributed by selected Contract Manufacturing Organisation.

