## 8 STUDY ASSESSMENTS AND PROCEDURES

- Study procedures and their timing are summarized in the SoA (Section 1.3). Protocol waivers or exemptions are not allowed.
- Immediate safety concerns should be discussed with the Sponsor immediately upon occurrence or awareness to determine if the subject should continue or discontinue study intervention.
- Adherence to the study design requirements, including those specified in the SoA (Section 1.3), is essential and required for study conduct.
- All screening evaluations must be completed and reviewed to confirm that potential subjects meet all eligibility criteria. The Investigator will maintain a screening log to record details of all subjects screened and to confirm eligibility or record reasons for screening failure, as applicable.
- Procedures conducted as part of the subject's routine clinical management (e.g., blood count) and obtained before signing of the ICF may be utilized for screening or baseline purposes provided the procedures met the protocol-specified criteria and were performed within the time frame defined in the SoA (Section 1.3).
- Some visits/study procedures may be done remotely via virtual visits (telemedicine) or at home health visits. Refer to Appendix 6 (Section 10.9) and Study Reference Manual for more details

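### Section 6.1's ±2-day window lets dose 2 or dose 3 fall five days after the previous dose, which Section 6.5.1's one-week minimum forbids; the window needs an anchor and no minus side

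*Combined protocol and SAP*

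**What the plan says.** **The minimum interval.** Section 6.5.1: "The first 3 doses will be administered at least 1 week apart". The only exception given is a delay because of a DLT. The paragraph opens with "All eligible subjects are planned to receive a minimal cumulative dose", so the rule is not confined to subjects under formal DLT assessment. For a subject without a DLT, the release step sets the second "dose at Week 1 (Day 8".

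**The DLT periods.** Section 6.5 defines the first period as "1 week after the first dose (prior to administration of the second dose", and defines the second in the same way around doses 2 and 3. The Schedule of Activities (Section 1.3) agrees: "Period 1: 1 week after the 1st dose". Section 6.5 also limits the assessment: "The first 15 subjects will be assessed for DLT".

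**The window.** Section 6.1 prescribes weekly administration with a tolerance of ±2 "days for the first 3 weekly infusion and thereafter weekly with a range of -1 day to +7 days". It names no anchor and does not rule out the early side.

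**Text that might rank the rules.** Section 6.4 refers dosing to the Schedule of Activities. Section 8 makes adherence to that schedule a requirement and adds "Protocol waivers or exemptions are not allowed". Neither mentions the one-week minimum.

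**The concern.** The interval between the first doses decides how soon a subject in a first-in-human study is exposed again. Section 6.5.1 treats a week as the least time in which to look for toxicity before the next dose is released. Section 6.1, where site staff would look for administration instructions, lets the same dose be given up to two days early. At a five-day interval, a DLT period cannot both last a week and end before the next dose.

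A week also matters elsewhere in the protocol. The laboratory definition of tumour lysis syndrome in Section 10.8 counts abnormalities within 7 days of dosing, and Section 6.8.1 expects tumour lysis from a cellular therapy to be delayed. A dose at five days falls inside the 7-day window of the previous dose and blurs attribution between the two.

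In practice, two sites, or a site and its monitor, could classify the same five-day dose differently: within window under Section 6.1, a deviation under Section 6.5.1.

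**Working it through.** **Inputs**
- Minimum interval between the first three doses: 7 days (Section 6.5.1).
- Nominal schedule: Day 1, Week 1, Week 2 (Section 6.5.1).
- Window: ±2 days, anchor not stated (Section 6.1).
- Length of each DLT period: 1 week, ending before the next dose (Sections 6.5 and 6.5.1).

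The window row of the Schedule of Activities also shows ±2, but its columns are broken in the text available to me, so the point rests on Section 6.1.

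**Step 1: the plan's own figure.** Day 1 + 7 = Day 8 for dose 2, as Section 6.5.1 states. Day 1 + 14 = Day 15 for dose 3. Nominal intervals are 7 and 7 days.

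**Step 2: apply the window.** Let a and b be the whole-day offsets of doses 2 and 3, each from -2 to +2.

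| Quantity | Window from previous dose | Window from Day 1 |
|---|---|---|
| Dose 1 to dose 2 | 7 + a = 5 to 9 days | 7 + a = 5 to 9 days |
| Dose 2 to dose 3 | 7 + b = 5 to 9 days | (14 + b) - (7 + a) = 7 + b - a = 3 to 11 days |
| Dose 1 to dose 3 | 10 to 18 days (14 nominal) | 12 to 16 days (14 nominal) |

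The first interval does not depend on the anchor, because Day 1 is the previous dose. A five-day second interval is reachable under either anchor. An interval shorter than five days needs the Day 1 anchor; the extreme is dose 2 on Day 10 and dose 3 on Day 13.

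**Step 3: shortfall.** At five days, 7 - 5 = 2 days are lost, or 2/7 = 29% of the one-week period.

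**Step 4: where both rules hold.** Section 6.5.1 requires at least 7 days. Counted from the previous dose, Section 6.1 allows at most 7 + 2 = 9. The overlap is 7 to 9 days, so only the 0 to +2 side of the window can be used.

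**Step 5: who is affected.** Section 9.1 plans approximately 60 subjects. Section 2.3.1 reports more than 15 enrolled and given 3 to 6 doses by 19 September 2022. That leaves fewer than about 60 - 15 = 45. This is an upper bound, since the number dosed after that date is not given.

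**Step 6: test the fix.** With -0/+2 from the previous dose, both intervals are 7 to 9 days and dose 1 to dose 3 spans 14 to 18 days. With -0/+2 from Day 1, the second interval is 7 + b - a with a and b from 0 to 2, which is 5 to 9 days, so the breach would remain.

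**The case against.** The strongest reply is that the rules do not truly collide. A careful site can satisfy both at 7 to 9 days. Meeting one requirement does not excuse breaching another, so a five-day dose remains a breach of Section 6.5.1, and Section 8 bars waivers. This stands, and it limits the claim: the protocol, read as a whole, does not authorise dosing at five days. It does not remove the problem, because a site following Section 6.1 would see the dose as in window and would not think a waiver was needed.

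A second reply is that *at least* may be loose drafting for *about*. The synopsis describes dosing as approximately weekly, and an exception for delay sits oddly beside a minimum. On that reading ±2 days is an ordinary visit window. This may explain the wording, but no text adopts it, and Sections 6.5 and 6.5.1 still ask for a week of observation before the next dose.

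A third reply points to other protection: staggered first subjects, DSMB clearance after the first three per cohort, clinic observation and telephone contact, and the suspension rules in Section 7.1. These lower the risk, and Section 2.3.1 reports no treatment-related events. None of them sets the interval.

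A reader might also infer that a shortened period hides Grade 4 neutropenia, which counts as a DLT only at 7 days or longer. The documents do not support adding that here. Section 6.5 counts the start of an event as well as its occurrence. Section 7.2 stops treatment for related life-threatening Grade 4 events, Section 8 calls for immediate discussion of safety concerns with the Sponsor, and Section 8.2.4 requires clinically significant abnormal laboratory tests to be repeated. What gap remains is narrow and separate, and a 7-day interval would not close it.

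**Conclusion.** The inconsistency is real, is in current text, and should be corrected. Section 6.1 read alone allows dose 2 or dose 3 five days after the previous dose, 2 days short of the week that Section 6.5.1 requires. This assumes that a week means 7 days, that offsets are whole days, and that the window is two-sided, as Section 6.1 writes it.

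Two stronger readings are not supported. One is that the second interval may be as short as three days. That needs a window counted from Day 1, which the text does not state, together with a late dose 2 and an early dose 3; weekly dosing ±2 days reads at least as naturally from the previous dose. The other is that the DLT data are compromised. The documents give no actual dosing dates and do not show that any subject was dosed early. Formal DLT assessment is confined to the first 15 subjects, and more than 15 had already been dosed by 19 September 2022.

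The consequence is therefore prospective: it concerns when subjects still to be treated may be re-dosed, because the interval rule is written for all eligible subjects.

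**What to change.** In Section 6.1, and in the window row of the Schedule of Activities to match, specify doses 2 and 3 at 7 days (-0/+2) after the previous dose. State the anchor explicitly, since the same window counted from Day 1 would still allow a five-day second interval. Delay for a DLT under Section 6.5.1 continues to apply.

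The cost is a change of wording in two places, a scheduling window of 3 days instead of 5 for each of doses 2 and 3, and an occasional delayed dose. DLT data already collected are unaffected.
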